16.3 Sponsor Records

Medtronic must maintain the following accurate, complete, and current records:

- All correspondence which pertains to the investigation
- Signed Investigator agreements, financial disclosure and current curriculum vitae of Principal Investigator and key members of the investigational site team
- Delegated task list
- All signed and dated CRFs submitted by Investigator, including reports of AEs, ADEs and device deficiencies

- All approved informed consent templates and other information provided to the subjects as well as advertisements, including translations
- Copies of all IRB approval letters and relevant IRB correspondence and IRB voting list/roster/letter of assurance
- Names of the institutions in which the clinical study will be conducted
- FDA correspondence, notification and approval
- Names/contact addresses of monitors
- Statistical analyses and underlying supporting data
- Final report of the clinical study
- The CIP, Report of Prior Investigations Summary and study related reports, and revisions
- Study training records for site personnel and Medtronic personnel involved in the study

16.4 Sponsor Reports

Medtronic must prepare and submit the following complete, accurate, and timely reports listed in Table 9 below. In addition to the reports listed below, Medtronic must, upon request of reviewing IRB or FDA, provide accurate, complete and current information about any aspect of the investigation.

Table 9: Sponsor Reports

Report	Submit to	Description/Constraints
UADE	FDA, IRBs, and Investigators	A sponsor who conducts an evaluation of an unanticipated adverse device effect under 812.46(b) shall report the results of such evaluation to FDA and to all reviewing IRBs and participating investigators within 10 working days after the sponsor first receives notice of the effect. Thereafter the sponsor shall submit such additional reports concerning the effect as FDA requests.
Withdrawal of IRB Approval	FDA, IRBs, and Investigators	A sponsor shall notify FDA and all reviewing IRBs and participating investigators of any withdrawal of approval of an investigation or a part of an investigation by a reviewing IRB within 5 working days after receipt of the withdrawal of approval (21 CFR 812.150(b)(2))
Withdrawal of FDA Approval	IRBs and Investigators	A sponsor shall notify all reviewing IRBs and participating investigators of any withdrawal of FDA approval of the investigation, and shall do so within 5 working days after receipt of notice of the withdrawal of approval. (21 CFR 812.150(b)(3))
Investigator List	FDA	A sponsor shall submit at 6-month intervals, a current list of the names and addresses of all investigators participating in the investigation. (21 CFR 812.150(b)(4))
Progress Reports	IRBs and FDA	Progress reports will be submitted at least annually. (21 CFR 812.150(b)(5), 812.36(f)

Report	Submit to	Description/Constraints
Recall and Device Disposition	FDA and IRBs	A sponsor shall notify FDA and all reviewing IRBs any request that an investigator return, repair, or otherwise dispose of any units of a device. Such notice shall occur within 30 working days after the request is made and shall state why the request was made. (21 CFR 812.150(b)(6))
Final Report	FDA, IRBs, and Investigators	The sponsor shall notify FDA within 30 working days of the completion or termination of the investigation. The sponsor shall submit a final report to the FDA, investigators, and all IRBs within 6 months after completion or termination of this study. (21 CFR 812.150(b)(7))
Failure to Obtain Informed Consent (prior to investigational device use)	FDA	Investigator's report of use of investigational device without obtaining consent will be submitted to FDA within 5 working days of notification. (21 CFR 812.150(b)(8))
Study Deviation	Investigators	Ensure that all deviations from the Clinical Investigational Plan are reviewed with the appropriate clinical investigator(s), are reported on the case report forms and the final report of the clinical investigation. Site specific study deviations may be submitted to investigators periodically.
Other	IRB, FDA	Accurate, complete, and current information about any aspect of the investigation. (21 CFR 812.150(b)(10))

Medtronic records and reports will be maintained in a password-protected document management system, and paper documents (where applicable) will be stored in secured file cabinets at Medtronic during the course of this study.

After closure of the study Medtronic will archive records and reports per standard operating procedure.

Appendix C: Engel Classification of Postoperative Outcomeⁱ

Class I: Free of disabling seizures^a

- A. Completely seizure free since surgery
- B. Nondisabling simple partial seizures only since surgery
- C. Some disabling seizures after surgery, but free of disabling seizures for at least 2 vears
- D. Generalized convulsions with AED discontinuation only

Class II: Rare disabling seizures ("almost seizure free")b

- A. Initially free of disabling seizures but has rare seizures now
- B. Rare disabling seizures since surgery
- C. More than rare disabling seizures since surgery, but rare seizures for the last 2 years
- D. Nocturnal seizures only

Class III: Worthwhile improvement^c

- A. Worthwhile seizure reduction
- B. Prolonged seizure-free intervals amounting to greater than half the followed-up period, but not <2 years

Class IV: No worthwhile improvement

- A. Significant seizure reduction
- B. No appreciable change
- C. Seizures worse

^aExcludes early postoperative seizures (first few weeks). This exclusion is quantitatively defined as 30 days for this protocol.

b"Rare" is quantitatively defined as ≤2 seizure days per year for this protocol.

^cDetermination of "worthwhile improvement" will require quantitative analysis of additional data such as percentage seizure reduction, cognitive function, and quality of life. This is defined as 80% reduction in seizures for this protocol.

Engel J. Outcome with respect to epileptic seizures. In *Surgical Treatment of the Epilepsies*, edited by J. Engel, Jr. Raven Press, New York. 1987

Appendix D: Data Monitoring Committee (DMC)

Point	Examples		
DMC will be used	Ongoing oversight for this study will be provided by an independent Data Monitoring Committee (DMC).		
Who will be involved	The DMC will have one statistician, at least one physician specializing in neurosurgery, at least one physician specializing in neurology, and one neuropsychologist. None of the DMC members are participating in the SLATE study. A chairperson from among those members will be identified.		
Responsibility of the DMC	 The DMC will be responsible for the following: Monitoring subject safety through review of aggregate clinical study data and adverse events Acting as an advisory panel on study design, study materials, study conduct, and subject safety issues Ensuring continued scientific validity and necessity, and making recommendations for protocol modifications Investigating root cause of missing data to minimize potential bias (i.e., screen failures, lost-to-follow-up, discontinuation from treatment) Evaluating issues associated with the procedural aspects of the clinical trial (e.g., slow enrollment) and providing recommendations for their resolution 		
Recommendations	The DMC will be advisory to the sponsor. The DMC may provide recommendations for continuation of the study, or early termination due to futility or safety concerns, or early attainment of study objectives. NOTE: Approval to proceed with the study or discontinue the study must be determined by a consensus of the DMC		

A DMC charter will be developed prior to the first subject enrollment.

The DMC will meet (via teleconference or in person) prior to the first subject enrollment to establish procedures for safety data review, chairman appointment, and guidelines for study recommendations. The DMC will meet on a periodic basis to perform data review, including at a minimum, all SAEs and deaths, and will meet more frequently when needed. DMC meetings may consist of both open and closed sessions. Medtronic personnel may facilitate the DMC meetings but will not have voting privileges.

Appendix E: Foreseeable Adverse Event List

The information provided in this section pertains to foreseeable adverse events that may be observed in SLATE study subjects and may assist in identifying those events for a given device or therapy that are unexpected in nature. The foreseeable adverse events information is based on AEs reported in published literature, the FDA Manufacturer and User Facility Device Experience (MAUDE) database, and Medtronic complaint handling system. Information regarding foreseeable adverse events may be used in combination with device labeling, current event reporting information, and other published data to assess for an unexpected occurrence.

The Visualase procedure involves surgery; therefore, standard events associated with a surgical procedure may be experienced (including but not limited to anesthesia complications, injury, infections, bleeding, exacerbation of pre-existing conditions, healing complications, and the unavoidable events listed in Section 10.1 of this Clinical Investigational Plan). Additionally, the patient population eligible for inclusion in this study has an underlying disease of epilepsy; therefore, standard events associated with epilepsy may be experienced (including but not limited to seizures, injury resulting from seizures and sudden unexpected death in epilepsy). However, the focus of this section is to specifically address in more detail, those events that are foreseeable due to the use, performance, and/or presence of the system under investigation.

Potential risks associated with the Visualase procedure as well as risk minimization are discussed within Section 11. Treatment required for procedure- and/or device- related adverse events that are experienced may include medication, surgical abandonment, or other surgical and medical remedies.

Observed Adverse Device Effects in Previous Clinical Studies

There have been no previous Medtronic-sponsored clinical studies evaluating use of the Visualase system for treatment of temporal lobe epilepsy.

Adverse Events in Literature & Post-market Event Reporting

The foreseeable adverse events associated with the Visualase procedure have been documented in various literature articles and in post-market event reporting. The foreseeable adverse events may include events that are possible but have not yet been reported. Adverse events associated with the Visualase System include, but are not limited to, the following:

- Anxiety
- Aphasia
- Back pain
- Blurry vision
- Brain abscess
- Bruising/ ecchymosis
- Cerebral vascular accident (CVA)

- Cerebrospinal fluid (CSF) leakage
- Death
- Deep venous thrombosis (DVT)
- Depression
- Device fragment retained in body
- Diplopia
- Edema

- Emotional lability
- Fever
- Headache
- Hematoma
- Hemianopia
- Hemiparesis
- Hemorrhage
- Herniation
- Hydrocephalus

- Infection
- Memory impairment / difficulty
- Meningitis
- Nausea
- Neurologic deficits
- Pain at incisional/access site

- Pain/discomfort/ stiffness
- Paralysis
- Persistent vegetative state
- Psychological/ psychiatric complications
- Pulmonary embolism (PE)
- Quadrantanopia

- Scalp numbness
- Scalp pain
- Seizure
- Sensory loss
- Skin abrasion or blister
- Sleep problems or insomnia
- Superficial wound infection
- Vomiting

Appendix F: Qualifying Primary Safety Endpoint Adverse Events

Adverse events will be reported per Section 10. Study Reportable AEs will count toward the primary safety endpoint if they qualify as follows:

- 1. Are device-, procedure-, or anesthesia-related; and
- 2. Are moderate or severe: and
- 3. Are permanent, for the following adverse events: anxiety, aphasia, blurry vision, depression, diplopia, emotional lability, hemianopia, hemiparesis, memory impairment/difficulty, neurologic deficits, paralysis, psychological/psychiatric complications, quadrantanopia, sensory loss, sleep problems or insomnia

Note: Transient events were not included in the literature analysis referenced as the performance threshold for the primary safety endpoint.³⁰

Figure 7 is a flow-chart to determine if a Study Reportable AE qualifies for inclusion in the primary safety endpoint analysis.

[figure not shown]

Figure 7: Qualifying Primary Safety Endpoint AE Flow Chart

Appendix G: Preliminary Publication Plan

Publications from the SLATE study will be handled according to Medtronic Standard Operating Procedures and as indicated in the Clinical Trial Agreement.

This study will be registered and results posted on www.clinicaltrials.gov. Medtronic, as the Sponsor, has proprietary interest in this study. Authorship and manuscript composition will reflect joint cooperation between study investigators and Medtronic personnel. Authorship will be established prior to the writing of the manuscript via a publication committee. The publication committee will develop the final publication plan as a separate document. As this study involves multiple sites, no individual publications will be allowed prior to completion of publication submission of the multicenter study except as agreed with Medtronic.

Appendix H: Other Documents

The following Clinical Investigational Plan documents will be provided separately:

- Device Labeling
- Informed Consent Form template
- List of Investigational Sites
- List of Institutional Review Boards
- SLATE Study Visualase Technique Recommendations
- SLATE Neuroimaging Manual of Operations
- SLATE Neuropsychological Manual of Operations
- SLATE Neuro-ophthalmologic Manual of Operations

Appendix I: Modifications to the Clinical Investigational Plan

Table 10 summarizes modifications made to the CIP.

Table 10: Change History

Version & Date	Applicable Sections	Change	Rationale	
1.0 16 June 2016	All	Initial Release	N/A	
2.0 19 July 2017	See Summary of Changes version 1.0 to 2.0	See Summary of Changes version 1.0 to 2.0	See Summary of Changes version 1.0 to 2.0	
3.0 26 July 2017	See Summary of Changes version 2.0 to 3.0	See Summary of Changes version 2.0 to 3.0	See Summary of Changes version 2.0 to 3.0	
4.0 09 April 2018	See Summary of Changes version 3.0 to 4.0	See Summary of Changes version 3.0 to 4.0	See Summary of Changes version 3.0 to 4.0

The purpose of this study is to evaluate the safety and efficacy of the Visualase System for necrotization or coagulation of epileptogenic foci in patients with intractable mesial temporal lobe epilepsy (MTLE). To assess safety, the primary endpoint will measure the incidence of qualifying device-, procedure-, or anesthesia-related adverse events (AEs) through 12 months following the Visualase procedure. To assess efficacy, the primary endpoint will evaluate seizure freedom (defined as Engel Class I) at 12 months following the Visualase procedure.

This is a prospective, single-arm, multicenter, investigational clinical study. The study is expected to be conducted at up to 25 sites located in the United States. A minimum of 150 subjects will undergo the Visualase procedure and be evaluated for a 12-month follow-up. To account for attrition, up to 215 subjects may be enrolled to ensure at least 150 subjects are treated with the Visualase procedure and complete the study requirements.

Revision 1.0

Page 4 of 23

Following enrollment, subjects' qualification for the Visualase procedure will be confirmed by a central review committee. Baseline assessments will also be performed at any time prior to the Visualase procedure. Study subjects will be followed for 12 months following the Visualase procedure.

The purpose of this statistical analysis plan (SAP) is to provide a comprehensive description, prior to the database lock and data analysis, of the statistical methods and analyses to be used for inclusion in the final study report. Analysis included in the final study report may be used to produce publications per the Stereotactic Laser Ablation for Temporal Lobe Epilepsy (SLATE) Publication Plan. No formal interim analysis is planned. Any interim monitoring of safety data will be conducted under the auspices of a data monitoring committee (DMC) assigned to this study.

The following document was used to create this SAP:

• SLATE Clinical Investigational Plan (CS-05000 Version 4.0, 09 April 2018)

4. Study Objectives and Endpoints

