14 STATISTICAL METHODS AND DATA ANALYSIS

14.1 Sample Size Determination

Subjects will be considered enrolled upon the signing of a consent form. It is anticipated that once enrolled, some subjects will not proceed to the Visualase procedure due to failure at their pre-surgical evaluation, changes in clinical status, or non-compliance to protocol. Based on these factors, and on previous reports of attrition in similar studies, the assumed attrition rate is 30%. To account for this attrition, up to 215 subjects may be enrolled to ensure at least 150 subjects are treated with the Visualase procedure.

The primary efficacy endpoint is the 12-month seizure-free rate. The analysis of the primary efficacy endpoint will include a point estimate and exact 95% confidence interval (CI) of the rate. The lower bound of the 95% CI of the seizure freedom rate following the Visualase procedure must be above 43%. Based on published and unpublished accounts of seizure freedom rates following laser ablation for MTLE, it is expected that approximately 56% of subjects who undergo the Visualase procedure will be seizure free through 12 months post procedure. Given these assumptions, 89% power can be achieved with data from 150 treated subjects.

Certain secondary endpoint assessments will be made using subject questionnaires. These self-reported instruments are influenced by primary language. Validated translations are not available in all languages, thus enrollment will be limited to subjects who can complete these assessments in either English or Spanish. Further, the impact of grouping across translations for analysis is an important consideration. Therefore, for the specified secondary cognitive and QOL endpoints, the subset of only the Englishlanguage versions will be used for analysis. To preserve adequate statistical power for analysis of this subset, the total Spanish language enrollment will be restricted to no more than 40% of the total study-wide enrollment population.

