The primary efficacy endpoint is the 12-month seizure-free rate. The analysis of the primary efficacy endpoint will compare the lower 2-sided exact 95% confidence interval (CI) boundary of the observed rate against 43%. The lower bound of the seizure freedom rate CI following the Visualase procedure must exceed 43%. Based on published and unpublished accounts of seizure freedom rates following laser ablation for MTLE, it is expected that approximately 56% of subjects who undergo the Visualase procedure will be seizure free through 12 months post-procedure. Given the assumption of a 56% success rate with Visualase, 89% power can be achieved with 150 treated subjects to show that the success rate after Visualase is superior to 43%.

Subjects will be considered enrolled upon the signing of a consent form. It is anticipated that once enrolled, some subjects will not proceed to the Visualase procedure due to failure at their pre-surgical evaluation, changes in clinical status, or non-compliance to protocol. Based on these factors, and on previous reports of attrition in similar studies, the assumed attrition rate is 30%. To account for this attrition, up to 215 subjects may be enrolled to ensure at least 150 subjects are treated with the Visualase procedure.

Certain secondary endpoint assessments will be made using subject questionnaires. These self-reported instruments are influenced by primary language. Validated translations are not available in all languages; thus, enrollment will be limited to subjects who can complete these assessments in either English or Spanish. Further, the impact of grouping across translations for analysis is an important consideration. Therefore, for the specified secondary cognitive and QOL endpoints, the subset of only the English-language versions will be used for analysis. To preserve adequate statistical power for analysis of this subset, the total Spanish language enrollment will be restricted to no more than 40% of the total study-wide enrollment population. A 40% cap was chosen based on a conservative assumption that only 73% of subject data are usable, resulting in an evaluable sample of N=109. If only 50% of this sample were used for secondary endpoints restricted to English language (N=55), the power to detect a change in the neuropsychological assessments would be 86%, based on best-estimate effect size.

7. General Statistical Considerations

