7.1.3.2 Modified Intent to Treat (mITT) Population

All subjects who enter the operating room and start the Visualase procedure (i.e., undergo scalp incision) will be included in the mITT analysis population. The mITT population will be the primary analysis population for efficacy evaluations.

Non-compliance is defined as any subjects who have not submitted enough seizure diaries or qualifiers in their seizure diaries through 12 months, from which the Engel I Classification could not be determined at study exit because of the missing information. The detail of the seizure diaries refers to section 7.5.1 of CIP.

SLATE Statistical Analysis Plan Revision 1.0 Page 9 of 23 Medtronic

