7.4 Handling of Missing, Unused, and Spurious Data and Dropouts

7.4.1 Missing Data

Missing primary efficacy endpoint values and missing secondary endpoint values associated with testable hypotheses will be imputed for analysis with the mITT analysis population. Missing primary efficacy endpoint data will be imputed as a binary outcome of seizure freedom, regardless of missing pattern. No daily level imputation will be conducted.

The primary method of imputation will be multiple imputation (SAS PROC MI followed by MIANALIZE). Ten repetitions will be performed and, if needed, will be increased until the algorithm converges.

The Markov chain Monte Carlo (MCMC) method or Fully Conditional Specification (FCS) will be used with the default number of burn-in iterations before the imputation. The model variables will include: age, sex, race (white, African American, or other), and duration of disease.

SLATE Statistical Analysis Plan		Form
Revision 1.0	Page 10 of 23	Medtronic

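### The SAP introduction says 215 enrolled ensures 150 treated completers, but the 30% attrition covers only loss before the procedure; SAP Section 6 also states 89% power without the protocol's condition that outcome data are available.

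*SAP*

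**What the plan says.** **What 215 is meant to deliver.** The SAP introduction states that "up to 215 subjects may be enrolled to ensure at least 150 subjects are treated with the Visualase procedure and complete the study requirements". The sentence before it also speaks of at least 150 subjects having the procedure and being evaluated over a 12-month follow-up.

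SAP Section 6 derives the number differently. It expects that "some subjects will not proceed to the Visualase procedure due to failure at their pre-surgical evaluation, changes in clinical status, or non-compliance to protocol", assumes attrition of 30%, and concludes: "To account for this attrition, up to 215 subjects may be enrolled to ensure at least 150 subjects are treated with the Visualase procedure". Protocol Section 14.1 gives the same reasons, rate and target. Neither section mentions completion.

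**What the 89% is conditional on.** SAP Section 6 says that, at an expected 56% seizure freedom, "89% power can be achieved with 150 treated subjects to show that the success rate after Visualase is superior to 43" percent. Protocol 14.1 says: "Given these assumptions, 89% power can be achieved with data from 150 treated subjects".

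**What the plan expects after the procedure.**
- Protocol Section 7.19 lists loss to follow-up and withdrawal among the reasons for exit.
- SAP Section 7.1.3.2 defines non-compliance by seizure diaries "from which the Engel I Classification could not be determined at study exit because of the missing information".
- SAP Section 7.4.1 provides that "Missing primary efficacy endpoint data will be imputed as a binary outcome of seizure freedom, regardless of missing pattern".
- SAP Section 7.4.3 handles deaths as lost to follow-up, except that a seizure-related death may not be imputed as seizure free.

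**The concern.** The number 150 carries three meanings: subjects treated (SAP 6, protocol 14.1), subjects treated who also complete the study (SAP introduction), and subjects contributing data (the power sentence in protocol 14.1). They coincide only if nobody is lost after the procedure. The enrolment calculation supports the first meaning, and the power calculation needs the third.

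A reader of the introduction would therefore expect 150 completers from 215 enrolled, which the plan's own attrition rate does not give. A reader of SAP 6 alone could take 89% as the power with 150 treated subjects however many outcomes are missing. What is at stake is the accuracy of two stated figures in the SAP. The test and its success criterion are not in question.

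**Working it through.** **Inputs.** From SAP 6 and protocol 14.1: null rate 43%, expected rate 56%, two-sided exact 95% confidence interval, 150 subjects, 30% attrition, 215 enrolled. The documents give no post-procedure loss rate and no missing rate for the primary endpoint. The 2%, 5% and 10% used below are assumptions.

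**1. Reproduce the enrolment figure.** Enrolled = treated / (1 − attrition) = 150 / 0.70 = 214.3, rounded up to 215. In reverse, 215 × 0.70 = 150.5 treated. Both agree with the plan.

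**2. Completers from 215, with 30% lost before the procedure.** Completers = 150.5 × (1 − later loss).
- 5% later loss: 150.5 × 0.95 = 143.0
- 10% later loss: 150.5 × 0.90 = 135.5, so 135

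**3. When the introduction would hold.** 150 completers from 215 allows a total loss of 65/215 = 30.2%. If the loss before the procedure were smaller than assumed, room for later loss = 1 − 150/treated.
- 25% before the procedure: 215 × 0.75 = 161.25 treated, room 7.0%
- 20% before the procedure: 215 × 0.80 = 172 treated, room 12.8%

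**4. Reproduce the power.** Success requires a count k whose two-sided 95% Clopper-Pearson lower limit exceeds 0.43. For n = 150 the smallest such k is 77 (lower limit 0.4305). Power = P(X ≥ 77 | n = 150, p = 0.56) = 89.1%. The plan's 89% is confirmed for 150 observed outcomes.

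**5. Power with fewer observed outcomes.** Exact power is saw-toothed in n:

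| n observed | k | Power |
|---|---|---|
| 150 | 77 | 89.1% |
| 149 | 77 | 87.4% |
| 148 | 76 | 88.9% |
| 143 | 74 | 86.6% |
| 142 | 74 | 84.6% |
| 135 | 70 | 85.5% |

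A single n can therefore mislead. Averaging over the number observed, taken as Binomial(150, 1 − m) with m the missing proportion, gives:
- m = 2%: 87.2%
- m = 5%: 85.6%
- m = 10%: 84.2%

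The baseline must be smoothed in the same way, because n = 150 is a local peak (n = 151 gives 87.6%). Local averages and a quadratic fit put smoothed power near n = 150 at about 87.7% to 87.9%. Like for like, the loss is about 2 points at 5% missing (87.8 − 85.6 = 2.2) and about 3.5 to 4 points at 10% (87.8 − 84.2 = 3.6).

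These figures assume outcomes missing completely at random, analysis of observed outcomes only, and no recovery of information from imputation.

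**The case against.** **This is wording.** The two operative sample-size sections agree on 215, 30% and 150 treated, and both headline figures are right. That stands: there is no arithmetic error. It does not remove the conflict, because the introduction uses the word ensure for a number that the calculation does not give at its own assumption.

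**215 is a ceiling and actual loss may be lower.** Also true: below 30% loss before the procedure, 150 completers is possible (step 3). If 30% was meant as total loss, then SAP 6 and protocol 14.1 are the places to correct. The passages need reconciling on either reading.

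**The planned analysis keeps all treated subjects.** The primary efficacy set is everyone with a scalp incision, and missing outcomes are multiply imputed, so the analysed count stays at 150. This is the strongest objection, and it limits the power figures: they approximate an observed-only analysis and do not describe the planned one. Keeping the count does not necessarily restore the information, however. SAP 7.4.1 says "The model variables will include: age, sex, race (white, African American, or other), and duration of disease", and unless those variables predict seizure freedom well, little is recovered.

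**Missingness may depend on outcome.** Retreatment or open resection already counts as failure (protocol 7.17), and a disabling seizure after day 30 generally settles the outcome too. Missingness completely at random is thus doubtful, and the true effect cannot be derived from the documents.

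**The protocol's condition can be read alongside the SAP.** The SAP names the protocol as its source and declares no changes to the planned analysis. That softens the point on power, but a SAP that restates the figure should restate its condition.

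**Conclusion.** The point holds as an inconsistency in stated figures. At the assumed 30% loss before the procedure, 215 enrolled gives about 150 treated, not 150 completers; about 143 or 135 would complete at an assumed 5% or 10% later loss. The 89% applies to 150 observed outcomes, as protocol 14.1 says and SAP 6 does not. Under the illustrative assumptions above, power is roughly 86% and 84% at 5% and 10% missing, a moderate loss.

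A reader might infer more, and the documents do not support it:
- **That 215 or 89% is wrong, or that enrolment must rise.** Both reproduce exactly, and the operative target is 150 treated.
- **That power falls by 3.5 or 5 points at 5% or 10% missing.** That subtracts averaged values from a saw-tooth peak; like for like it is about 2 and 3.5 to 4.
- **That the usable-data share of 73% (N = 109) in SAP 6 is the expected loss for the primary endpoint.** It is labelled conservative and is used only to justify the cap on Spanish-language enrolment. It does show that the SAP contemplates treated subjects without usable data.

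**What to change.** **SAP introduction.** Delete the completion clause and bring the preceding sentence, on evaluation over 12 months, into line with the 150-treated target of SAP 6 and protocol 14.1. Changing only the one clause would leave similar language beside it. Alternatively, state an assumed post-procedure loss and the number of completers that results.

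**SAP Section 6.** Restore the protocol's condition that the 89% rests on data from 150 treated subjects, and add that power is lower if outcomes are missing. Figures are optional. If given (about 86% at 5% and 84% at 10%, against a smoothed value of about 88%), mark them as illustrative, missing completely at random, and with no recovery from imputation.

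**Cost.** Wording in two places in the SAP. The stated power becomes conditional and slightly less favourable. Protocol 14.1 needs no change, provided the 30% is meant as pre-procedure loss, as it is described there.
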